3. STUDY DESIGN

LACI-3 will be an investigator-led, Phase III, prospective, randomised, controlled, 2x2 partial factorial, open label, blinded outcome trial performed in multiple UK hospital-based centres. LACI-3 is open to support international collaboration. The trial received Scientific Advice from the Medicines and Health Care Regulatory Agency assisted by NHS England Medicines Repurposing Programme at a meeting on 2nd July 2024. All MHRA guidance has been incorporated into the design of LACI-3.

Duration: The trial will last for 52 months with the treatment phase for each participant starting from within one day of randomisation until the end of trial follow-up at 18 months.

Participants meeting inclusion/exclusion criteria will be randomised at participating hospitals.

Participants will be randomised to start one of four treatments; ISMN only; cilostazol only; both ISMN and cilostazol; or neither ISMN nor cilostazol. Patients with contraindications to cilostazol can be randomised to ISMN versus no ISMN arms only; patients with contraindications to ISMN can be randomised to cilostazol versus no cilostazol arms only. The partial factorial design allows testing of both drugs when given alone and together. As in LACI-2, the doses will be escalated until participants are on their full dose by 1 month. If a patient encounters intolerable side effects at full dose, then they will be able to remain on the highest dose regime that they can tolerate and this dose will be recorded. The total duration of the trial drug administration will be 18 months. After the end of follow-up, the patients will reduce the tablets over about two weeks and then stop the trial medication. They will return any unused drug to their local community pharmacy or the hospital pharmacy if more convenient for destruction.

Drug supply: Trial drug will be dispensed by hospital pharmacies. The first drug supply will be given at the randomisation visit if allocated to the IMP. The IMP re-supply for the followup at 6 and 12 months will be posted to participants. Participants can collect the IMP resupply in person from the recruiting site.

Participants should continue their allocated treatment until the end of 18-month follow-up.

Discontinuing the allocated treatment by the participant's direct clinical care team due to the occurrence of an outcome event does not constitute withdrawal.

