Note that randomisation will be performed during normal office hours (09.00 - 17.00) and the trial allows for randomisation to occur any time beyond 24hrs after the stroke (if the eligibility criteria are met) with no upper time limit after the stroke. Therefore, in the event of computer failure (for example: server failure), the investigator will wait until the computer system is re-established to perform the randomisation. Normally, this would only be a few minutes to two hours. However, if this delay requires the patient to return on a separate occasion to collect the drugs, then a separate appointment will be made and the patient's travel expenses covered as per other trial visits or the drug supply may be sent by post for the next day delivery.

Patients will be randomised to one of the following at a 1:1 ratio as per Section 6.3:

- cilostazol versus no cilostazol
- ISMN versus no ISMN

resulting in a partial factorial comparison of cilostazol versus ISMN versus both drugs versus neither drug.

All participants will continue their usual prescribed guideline stroke prevention medication.

The randomisation algorithm will allocate a unique participant identifier which will be used to label the treatment pack containing the appropriate drug made up for the patient and dispensed by the local Pharmacy.

Participants with an indication for or contraindication to one of the trial drugs may still be randomised to the other trial drug. If a participant allocated to both trial drugs develops a contraindication to one of the trial drugs after randomisation into the trial, then they should discontinue that drug but continue to take the other trial drug. If a patient has to discontinue either or both drugs, they should continue to be followed up in the trial as planned (unless they withdraw from the trial). Patients should remain in follow up until the end of the trial follow up period, even if they discontinue trial drug, unless they withdraw from the trial. Drug discontinuation will be recorded.

The study will be performed open label. Placebo tablets are not available and masking by encapsulation is too complicated and expensive. However, blinding of outcomes is important to obtain unbiased information about tolerability, safety, and efficacy. As such, IMP adherence structured questionnaire and prescribed medications will be taken by site staff who are already unblinded to trial allocation, while ascertainment of the main cognitive and

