9. STATISTICS AND DATA ANALYSIS

9.1 SAMPLE SIZE CALCULATION

The primary outcome, cognitive impairment assessed using the DSM-5 7-level ordinal score, will be compared between ISMN vs no ISMN, cilostazol vs no cilostazol, and ISMN+cilostazol vs no ISMN or cilostazol using ordinal logistic regression adjusted for stratification and minimisation variables. The null hypothesis is that ISMN, alone or with cilostazol, will not reduce long-term cognitive impairment in patients with lacunar ischaemic stroke.

A sample of N=1300 is needed (650 ISMN, 650 no ISMN) assuming alpha 5%, power 90%; distribution of DSM-5 7-level ordinal score in the control (standard of care) group is: level 1 (normal): 35%, 2: 24%, 3: 12%, 4: 20%, 5: 3%, 6: 3%, 7 (dead):3% (as in LACI-2); DSM-5 7-level unadjusted odds ratio 0.70 (the risk reduction exceeds the minimal clinically important

difference [MCID] of 0.27), standard deviation 1.33; losses/cross-overs 15%; no covariate adjustment; sample rounded up

Notes:

1. We chose OR 0.70 because it represents a 'small' treatment effect and so is of relevance to the large lacunar stroke cSVD population; a readily available, easy to administer and inexpensive intervention, albeit with small (or better) effect, would be very valuable clinically. The odds ratio=0.70 is more conservative than that seen in LACI-2: ISMN vs no ISMN aOR 0.55 (95% CI 0.36, 0.86) and ISMN+cilostazol aOR 0.44(95%CI 0.23-0.85).⁴⁹

2. The MCID assumption of 0.27 lies in the range of 0.17 to 0.69, which is based on plausible values from anchor, distribution and expert opinion in dementia and stroke studies,⁶¹⁻⁶⁴ and calculated from LACI-2⁴⁹ and R4VaD, a large UK cohort study, n=2441, of post-stroke cognitive impairment.⁴⁸ The distribution-based MCID of 0.27 is based on pooled standard deviation (SD) of 1.33 in LACI-2, multiplied by 0.2, as appropriate for low cost drugs.⁶¹ The anchor-based MCID for DSM-5 7-level cognition at 1year in LACI-2 was 0.41 for ISMN v no ISMN,⁴⁹ and was 0.69 for severe vs. mild stroke in R4VaD, but this is less relevant to lacunar stroke (1^{ry} results in prep).⁴⁸ A survey of experts (n=48, ongoing) suggested an MCID of median 0.4-0.5.

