9.2 PROPOSED ANALYSES

All analyses and presentation of the results will be in accordance with CONSORT guidelines including on factorial trials.⁶⁶ All analyses will be intention to treat. A full statistical analysis plan will be developed and published prior to database lock including use of imputation or complete case analysis and sensitivity analyses. Numbers (%), median [interquartile range] or mean (SD) will be used as appropriate to summarise data, with 95% confidence intervals (CI). Main outcomes will be presented for the whole population and by sex. Participants who die will be included in the DSM-5 7 level ordinal cognitive and mRS scores, and for scores without a category for death will have a score worse than any living score assigned to maintain power and prevent missing any 'kill or cure' effect. Multiple testing adjustments will be used where relevant.

Analyses will use, as appropriate: binary logistic regression (BLR, presented as adjusted odds ratio, aOR), Cox proportional hazards regression (CPHR, adjusted hazard ratio, aHR), ordinal logistic regression (OLR, presented as aOR), or multiple linear regression (MLR, presented as adjusted mean difference, aMD). 95% confidence intervals (CI) will also be given.

Analyses will be adjusted for stratification (MoCA) and minimization variables (baseline age, sex, NIHSS, mRS, SBP, smoking status, time after stroke, years of education). Additional adjustments will be used where relevant and feasible, e.g. treatment duration, visible infarct y/n and SVD burden.

The Primary outcome is an ordinal adjusted analysis of the DSM-5 7-level cognitive score at 18 months.

Secondary outcomes will be analysed including all available data, using:

-*MLR*: 7-level ordinal mRS, 4-level DSM-5 cognitive score, cognitive tests individually (MoCA, TICS); Quality of Life (EQ-5D, Health Status Utility Value and VAS); mood (Zung); Stroke Impact Scale individual domains and overall score;

-BLR: dependency [mRS>2] vs no dependency; death; recurrent ischaemic or haemorrhagic stroke or TIA, or MI, individually; systemic haemorrhage; symptoms; SAEs, SARs, SUSARS – events that meet these definitions as per protocol and that are not already reported as formal outcomes;

-CPHR: death; and a Composite Outcome (recurrent stroke or TIA, MI, dependency [mRS>2], any cognitive impairment, death) using patients with complete data for all required variables, adjusted for baseline variables;

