-and the *Wei-Lachin test* (unadjusted), reported as *Mann-Whitney difference (MWD)*: a Global Clinical Outcome (recurrent ordinal stroke, ordinal MI, ordinal 7-level cognition, ordinal mRS, quality of life (full Health Status Utility Score of the EQ-5D), the Zung depression score full scale, and the binary status of alive or dead) using all patients; and a Global SIS score.

Subgroup analyses: Prespecified subgroups include all minimisation variables (baseline age, sex, NIHSS, mRS, SBP, smoking status, time after stroke, and years of education), hypertension, diabetes, prior stroke/TIA, index infarct on imaging, WMH score, SVD score, duration of treatment, for 7-level ordinal cognition, ordinal mRS, recurrent stroke or TIA. We will assess cognitive and dependency outcomes, recurrent vascular events, safety, QoL and HE usage at 6 and 12 months, using repeated measures where relevant. Subgroup analyses will be adjusted for cilostazol in ISMN models and for ISMN in cilostazol models to assess interactions. Other exploratory subgroup analyses may be performed.

Sensitivity analyses: Imputation analysis of primary outcome. Baseline characteristics of participants with versus without long term outcome cognition data (DSM-5 7 level ordinal score, tMoCA, TICS) and/or long-term dependency (mRS) to assess for drop-out bias. Composite Outcome, including all patients with any data for the required analysis, regardless of whether missing.

Missing data: The primary outcome (DSM-5) incorporates data from multiple sources and so suffers from less loss of data than when using a single outcome scale; Death is a valid outcome in DSM-5 and is not missing data; The sample size includes an inflationary adjustment for up to 15% missing primary outcome data; Baseline data and adherence will be compared for those with versus those without missing DSM-5 data.

A full Statistical Analysis Plan will be prepared and published during LACI-3 prior to data softlock, as was done for LACI-2, and will describe analysis procedures and procedures for missing, unused or spurious data, and definitions of populations analysed.

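### Protocol 9.2 uses time on treatment, which is settled after randomisation, as a prespecified subgroup and as an optional covariate

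*Protocol*

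**What the plan says.** Section 9.1 gives the primary model as a comparison of the 7-level ordinal cognitive score "using ordinal logistic regression adjusted for stratification and minimisation variables". Section 9.2 repeats that baseline adjustment set and then adds an open-ended sentence: "Additional adjustments will be used where relevant and feasible, e.g. treatment duration, visible infarct y/n and SVD burden".

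The subgroup paragraph of 9.2 lists the minimisation variables, some medical history items and imaging scores, and ends with "SVD score, duration of treatment, for 7-level ordinal cognition, ordinal mRS, recurrent stroke or TIA". The first outcome in that quote is the primary outcome. Duration is the only item on the list that is not a baseline characteristic.

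Three other statements bear on this:

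- Section 9.2: "All analyses will be intention to treat".
- Section 3: "The total duration of the trial drug administration will be 18 months".
- Section 5.5.1: "If a patient has to discontinue either or both drugs, they should continue to be followed up in the trial as planned".

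Section 6.2 states that there is no placebo and that the comparator is standard care. Neither list defines the duration variable.

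**The concern.** A covariate or subgroup variable preserves the randomised comparison only if treatment cannot affect it. Time on drug fails that test. It reflects tolerance, health and, in some participants, the outcome: death is level 7 of the primary score and ends treatment, and section 3 foresees the clinical team stopping trial drug because an outcome event has occurred. A short duration can therefore be the result of a bad outcome and not its cause.

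Two things are at stake. Splitting the drug arm by time on treatment sets selected adherers, or selected stoppers, against controls who were not selected in that way. That can produce an apparent gain from longer treatment, and the lay summary already suggests that the tablets may do more if taken for longer, so such a result would be easy to believe. Separately, any model that contains duration beside allocation answers a different question from the intention-to-treat one, and does so with poor precision.

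**Working it through.** **Step 1: which duration can be meant?**

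- *Planned duration.* It is 18 months for all (section 3). A constant can neither adjust a model nor define a subgroup.
- *Realised time on the drug under test.* It varies through discontinuation with continued follow-up (section 5.5.1). With no placebo it is zero for participants not allocated that drug. The zero is not written; it follows from the design. A stratum such as 12 months or more on drug then contains no controls, so no within-stratum comparison or interaction can be estimated.
- *Realised time on any trial drug.* In the ISMN contrast, cilostazol-only participants would have non-zero values. The variable is still settled after randomisation, so the comparison is still broken.

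**Step 2: reproduce the plan's sample size.** Inputs from 9.1: control distribution 35/24/12/20/3/3/3%, odds ratio 0.70, alpha 5% (taken as two-sided), power 90%, losses 15%.

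Applying 0.70 to the control distribution gives 43.5/23.8/10.5/15.8/2.2/2.2/2.1% on drug. With p̄ the mean of the two distributions, 1 − Σp̄³ = 0.919. The Whitehead proportional-odds formula gives

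N = 12(1.960 + 1.282)² / [(ln 0.70)² × 0.919] = 12 × 10.507 / (0.1272 × 0.919) ≈ 1079 evaluable.

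Dividing by 0.85 gives 1270, consistent with 1300 after rounding up. At 1300 × 0.85 = 1105 evaluable, SE(log OR) = √[12 / (1105 × 0.919)] = 0.109. Power = Φ(0.357/0.109 − 1.96) ≈ 91%.

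**Step 3: precision lost by adding duration.** Let duration be a fraction of 18 months, zero without the drug, with mean m and variance v in the drug arm. With 1:1 allocation, the squared correlation of allocation with duration is m²/(m² + 2v), so

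variance inflation = 1 + m²/(2v).

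Assume that a fraction s stops at a uniform time. Then m = 1 − s/2 and v = s/3 − s²/4. The documents give no stopping pattern, so s is shown as a range.

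| s | m | v | Inflation | SE(log OR) | Power at OR 0.70 |
|---|---|---|---|---|---|
| 10% | 0.95 | 0.0308 | 15.6 | 0.43 | 13% |
| 20% | 0.90 | 0.0567 | 8.1 | 0.31 | 21% |
| 30% | 0.85 | 0.0775 | 5.7 | 0.26 | 28% |

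SE = 0.109 × √inflation; power = Φ(0.357/SE − 1.96). The inflation formula is exact for a linear model and approximate here. Fitting the proportional-odds model directly over the same stopping range gave SEs of 0.26 to 0.43. The power column assumes that stopping is unrelated to prognosis and that the drug effect does not depend on time on drug.

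**Step 4: direction of bias with an inert drug.** Two simulations let frailer participants stop sooner and do worse. The true odds ratio is 1; values below 1 look like benefit.

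| Assumptions | Allocation OR with duration in model | Longer-treated vs all not allocated | Early stoppers vs all not allocated |
|---|---|---|---|
| 20–30% stop; frailty coefficient 0.8 on outcome, 0.5 on log odds of stopping | 1.45–1.5 | 0.89–0.92 (full duration) | 1.25–1.30 |
| Stopping set at 15, 25 or 40% at average frailty; coefficient 1.0 on both; death also ends treatment | 2.6–4.6 | 0.82–0.87 (12 months or more) | 1.7–2.5 (under 12 months) |

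The direction agrees. The sizes differ widely because the assumed link between stopping and prognosis differs.

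**The case against.** The strongest reply is that the confirmatory analysis is already protected. Section 9.1 fixes the primary model with stratification and minimisation variables only, and 9.2 repeats that set. Duration enters as one example in a sentence conditioned on relevance and feasibility. This stands. A reader might infer that the primary analysis is invalid, or that the trial's power falls to 13–28%. The documents do not support that: those figures describe an optional additional model.

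A reader might also infer that the protocol has abandoned intention to treat. It has not: the intention-to-treat contrast remains specified, and the duration subgroup is one of many secondary looks. The inconsistency is limited to these two items, which sit under a statement that covers all analyses.

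A second reply is that the variable is undefined and the SAP may define it. That is fair for a missing detail, and a by-visit reading is conceivable because the text goes on to repeated measures at 6 and 12 months. But duration is named as a subgroup variable, and neither constant planned duration nor realised duration gives a valid subgroup. An SAP that followed the list would inherit the fault, and one that dropped the item would depart from the protocol.

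A third reply is that the bias sizes in step 4 are not facts about this trial. That is correct. Only the near-duplication of allocation by duration and the empty control strata hold whatever is assumed about prognosis, given the likeliest reading of the variable.

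**Conclusion.** The point holds and is a should-fix. The firmer part is the subgroup: it is prespecified for the primary outcome and two others, contains no randomised comparison, and can yield a false finding that longer treatment is better. The covariate is the lesser part, because it is optional. Any model that used it would not estimate the intention-to-treat effect and, with 10–30% stopping early at a uniform time, would have variance inflation of about 16 down to 6 and power of about 13% up to 28%, against about 91% without it.

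Those figures rest on the assumed stopping pattern, 1105 evaluable participants and a duration of zero without the drug. The size of any bias cannot be stated from the documents. The main primary model is exposed by the loose wording but not invalidated.

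**What to change.** In section 9.2, and in the SAP:

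- delete duration of treatment from the subgroup list;
- delete treatment duration from the additional covariates;
- state that additional covariates are limited to variables fixed before randomisation, such as visible infarct and SVD burden on the baseline scan.

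If the effect of exposure is of interest, specify it as a separate analysis labelled exploratory, with its assumptions stated. A complier-average effect with allocation as instrument needs the exclusion restriction, which is questionable in an open-label trial without placebo. Reading it as an effect per month also needs linearity in time on drug. Deletion alone is sufficient if no such analysis is wanted.

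The cost is two deletions and one or two sentences before database lock. No new data are needed. The sample size was calculated without covariate adjustment and stays at 1300.

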6.9 STUDY ASSESSMENTS

Study assessments (see Table 2) include the maximum of the six planned study visits.

The first study visit includes consent, baseline information collection and randomisation. After eligibility confirmation and obtaining the informed consent, investigators will collect the baseline medical history data required for randomisation. The randomisation visit can take place on the same day as the consent visit at the clinic, if all required tests for eligibility criteria and the baseline information are available.

Baseline information will include the confirmation of eligibility and informed consent details, demographic information such as date of birth, sex assigned at birth, ethnicity, years of full-time education ^{62, 63} and occupation.

The medical history will contain details of incident stroke, past medical history, vascular risk factors, concomitant medications and the characteristics of the lacunar stroke and SVD features (white matter hyperintensities/hypoattenuation, and/or lacunes) on brain imaging.

Baseline brain MR (preferred wherever possible) or CT: To identify the index stroke or exclude other causes of symptoms, and assess the burden of SVD – this is the clinical scan with MRI (T2, FLAIR, T1, T2* or SWI and diffusion imaging) or CT obtained soon after the presentation with stroke to diagnose the stroke. Brain imaging in eligible patients with lacunar ischaemic stroke may show either:

- a recent, relevant (in time and location) acute small subcortical (lacunar) infarct,

- or, if no visible acute lacunar infarct, there is no other competing pathology as a cause for stroke (e.g. no acute cortical infarct, no intra-cerebral haemorrhage, no stroke mimic such as tumour, or subdural haematoma)... Investigators will post scans to the LACI-3 Imaging office in Edinburgh for central reading in DICOM format or upload them online to the database according to the imaging acquisition guidance.

In participants whose lacunar stroke occurred more than six months previously, or in whom there have been further neurological symptoms, any brain MRI or CT imaging performed in the interval between the index lacunar stroke and recruitment should also be sent for central reading.

Cognitive baseline testing: Participants will be assessed at baseline using the Montreal Cognitive Assessment (MoCA), and the timed Trail Making Test B for processing speed/executive function, and for the concentration, the backwards spelling from the MMSE.

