The lifestyle risk factors for vascular disease such as cigarettes and alcohol use as well as blood pressure, weight and height will be collected as a part of the baseline information.

Participants will be asked about health-related quality of life (using the EuroQol Group EQ-5D-5L/ EQ-VAS instrument).

Haematology and biochemistry: Full blood count, urea and electrolytes and renal function results will be obtained and collected on e-CRF from the most recent standard of care results sample since the time of the index stroke. If there is a clinical reason to expect change since this last sample, the full blood count and biochemistry should be repeated prior to randomisation. These samples will be analysed in the hospital haematology or biochemistry labs in the centre in which the patient has been recruited as a part of the standard clinical care.

Clinical outcomes: Information on recurrent ischaemic stroke, TIA, major systemic or brain haemorrhage, non-fatal MI, and dementia will be assessed by phone or post questionnaire at 6, 12, and 18 months as well as by checking the participant's medical notes. Patients will be encouraged to seek medical advice if they develop new neurological events during the trial. The death of any cause will be detected, reported and recorded by the investigators based on the information from the medical notes.

Functional outcome: modified Rankin Scale to assess dependency at 6, and 12, 18 months. If participants are unable to be contacted, the central assessor will obtain the most recent modified Rankin Score from the local staff (if available) or estimate from the relative/carer.

Cognitive and mood outcomes: Telephone MoCA (tMoCA), The Telephone Interview for Cognitive Status (TICS), animal naming, Concentration (from the MMSE), the ZUNG and Stroke Impact Scale (SIS), will be collected remotely at 6, 12 and 18 months by the central trial team.

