+/- 1	+/- 1 week				+/- 3 weeks			+/- 5 weeks					
Phone	one Pho	ne Phone	Post	Post	Phone	Phone	Post	Post	Phone	Phone	Post	Post	Phone
	1												
												٠	
•	• •	•				•				•			
		•				•				•			
			•				•						
•	•												
			٠				•						
										•			
•	• •			•				٠				•	
•	• •	•				•				•			
•	• •			•				•			•)	
										1			
				٠				•				٠	
					٠				٠				٠
•	• •			•				•			•)	
				٠				٠				٠	
					• • • •	• • • •	• • • • • • • • •		• •	• • • • • • • • • • • •	• • • • • • • • • • • • • • •	• • •	• •

^a Randomisation visit can take place on the same day as the consent visit at the clinic, if all required tests for eligibility criteria and the baseline information are available.

^b Participants will be followed up remotely by phone and post for 18 months by two teams: local site and the central research team.

^c End of Study Visit is a follow-up visit at 18 months.

^d Copy of the diagnostic scan (CT or MRI) will be sent for central reading.

⁶ Full blood count, urea and electrolytes and renal function will be obtained from the most recent sample since the time of the index stroke. ¹ Blood pressure collection is optional depending if a participant has access to the BP monitor or GP or hospital measure is available.

⁹ Dispensing in 3-monthly intervals is allowed. IMP re-supply to be sent to the participants home address.

^h Recurrent ischaemic stroke, TIA, major systemic or brain haemorrhage, fatal or non-fatal MI, death of any cause, dementia

¹ Modified Rankin Scale can be obtained from the relative/carer or the local site if a participant is unable to be contacted. ¹ Stroke Impact Scale (SIS), Telephone MOCA, Telephone Interview for Cognitive Status (TICS), concentration (from MMSE), Animal naming, ZUNG

* SAE - Serious Adverse Event; SAR - Serious Adverse Reaction, SUSAR - Suspected Unexpected Serious Adverse Reaction

¹EQ5D5L, EQ-VAS - quality of life questionnaires will be done at baseline and each follow-up visit. The NHS and social service use will be done at 18 months visit

^m Women of childbearing potential must have negative urine pregnancy testing on the day of randomisation. If applicable, the central team will send the urine pregnancy test with the central follow-up paper questionnaire.

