7.2 CASE REPORT FORMS

The electronic case report forms (eCRF) will be used to collect trial data. The web-based trial database will require user authentication with user-specific access rights for data entry, editing, and password protection. A separate database will be used to encrypt and store participants' personal identifiable data required to perform the follow-up. Paper versions of the

eCRF will assist with data collection when interviewing patients at baseline and during followup visits by phone or post. Research staff will file all completed paper CRFs in the ISF or TMF if data have not been entered directly on e-CRF.

Section 7.2 (study assessments) details data to be collected, including time points and who will collect data.

Baseline case report forms will include pre-randomisation and post-randomisation data collection.

Baseline eCRFs will contain:

- General eligibility criteria confirmation
- Cilostazol eligibility criteria confirmation
- ISMN criteria confirmation
- Investigator confirming eligibility and their role
- Informed consent details (date of the ICF, date of PIS given to participant, version of PIS and ICF, Investigator taking consent details and their role)
- Participant details (initials, date of birth, sex assigned at birth, ethnicity, years of fulltime education and occupation, employment status)
- Medical history (details of incident stroke, past medical history, vascular risk factors, concomitant medications and the characteristics of the lacunar stroke and SVD features on brain imaging.
- Medication list
- Lifestyle risk factors (smoking cigarettes and alcohol use)
- Falls
- Blood pressure, weight, and height
- Quality of life (5D-5L/ EQ-VAS)
- Cognitive testing (MOCA, Trail Making Test B, concentration MMSE)
- Participant contact details (name, postal address, telephone, email)
- Participant CHI/NHS Number
- GP contact details (name
- Optional: Participant close personal contact details to be used when the participant is uncontactable during follow-up (name, postal address, telephone, email, relationship)
- Date and time of randomisation

The participant, GP, and participant's CHI/NHS Number will be encrypted and be stored separately from the anonymised trial data in compliance with data protection regulations. The nominated close personal contact details collected on the paper Contact form will be stored securely only at the local hospital NHS research team.

Prescription eCRF will include:

- Date of prescription

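### Baseline EQ-5D-5L and EQ-VAS are collected but not named as covariates in the models for the same outcomes, which probably costs precision in the quality-of-life results

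*Protocol*

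**What the plan says.** **Collected at baseline.** Section 6.9 (baseline information): "Participants will be asked about health-related quality of life (using the EuroQol Group EQ-5D-5L/ EQ-VAS instrument". The baseline eCRF list in section 7.2 has "Quality of life (5D-5L/ EQ-VAS", and the footnote to the Study Assessments table in 6.9 says that the "quality of life questionnaires will be done at baseline and each follow-up visit". For cognition, 6.9 includes at baseline, "for the concentration, the backwards spelling from the MMSE", and the eCRF list has "Cognitive testing (MOCA, Trail Making Test B, concentration MMSE".

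**Secondary endpoints.** Section 2.2.2 lists EQ-5D-5L, EQ-VAS and MMSE concentration at 18 months.

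**Analysis.** Section 9.2 puts "Quality of Life (EQ-5D, Health Status Utility Value and VAS" in the multiple linear regression list. Analyses are to be adjusted for MoCA (the stratification factor) and for age, sex, NIHSS, mRS, systolic BP, smoking, time after stroke and years of education. It then adds: "Additional adjustments will be used where relevant and feasible, e.g. treatment duration, visible infarct y/n and SVD burden". A full SAP is promised before the data are locked.

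**Concentration.** Section 9.2 names no model for it. The individual cognitive tests in the linear regression list are MoCA and TICS.

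**The concern.** In a linear model for a continuous outcome, the participant's own baseline value is often the most informative covariate available. Here it is on the eCRF, but the covariate sentence does not commit to using it for quality of life.

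The protocol's own reasoning points the other way. The model for mRS contains baseline mRS, and the models for cognition contain baseline MoCA. Note 4 of section 9.1 says covariate adjustment improves power. Its one reservation concerns ordinal cognitive scales, which does not touch EQ-5D utility or EQ-VAS in linear regression.

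Quality of life is a stated secondary objective. In LACI-2 it gave a signal for the combination (adjusted mean difference 0.10, section 1.1). A confidence interval wider than the data require would weaken the test of that signal.

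**Working it through.** **1. The plan's own figure.** There is none for quality of life; the only sample size is for the primary ordinal outcome. The Whitehead proportional-odds formula, with the control distribution in 9.1, gives

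N = 12(1.96 + 1.282)² / [(ln 0.70)² × (1 − Σp³)] = 12 × 10.507 / (0.1272 × 0.9335) ≈ 1062 evaluable.

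With 15% losses this is 1062/0.85 ≈ 1249 or 1062 × 1.15 ≈ 1221. The power table states 1229, rounded up to 1300 in the text, so the figure reproduces. It assumes no covariate adjustment and does not depend on this point.

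**2. Inputs for the illustration.**
- From 9.1: 1300 randomised, 15% lost, so 1105 evaluable, about 552 per group on one factorial margin. Alpha is 5%, taken as two-sided.
- Assumed, not in the documents: SD 0.25 for EQ-5D utility (taken as the residual SD after the listed covariates), difference 0.04, and ρ, the partial correlation of baseline with 18-month value given those covariates.

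**3. Formula.** Adding the baseline value multiplies residual variance by 1 − ρ².

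Power = Φ( D / [SD × √(2/n) × √(1 − ρ²)] − 1.96 )

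With n = 552, the standard error without baseline is 0.25 × √(2/552) = 0.01505, and 0.04/0.01505 = 2.658.

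| ρ | Variance reduction | 95% CI half-width | Power at D = 0.04 |
|---|---|---|---|
| 0 | 0% | 0.0295 | 75.7% |
| 0.3 | 9% | 0.0281 | 79.6% |
| 0.5 | 25% | 0.0255 | 86.6% |
| 0.6 | 36% | 0.0236 | 91.4% |

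**4. A second route, through explained variance.** Suppose the listed covariates explain 10% and the baseline value raises this to 25%. Residual variance is multiplied by 0.75/0.90 = 0.833, and a comparison with 80% power reaches about 87%. Going from 20% to 40% gives 0.60/0.80 = 0.75 and about 90%. These shares are also assumptions.

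**5. A large effect.** Take the LACI-2 value of 0.10 for both drugs against neither. If everyone is randomised to both factors, there are 1300/4 × 0.85 ≈ 276 evaluable per arm. The standard error is 0.25 × √(2/276) = 0.0213, so power without any baseline term is Φ(4.70 − 1.96) = 99.7%. Almost nothing is left to gain. At 0.04 the same comparison has about 47% power without baseline and 58% at ρ = 0.5. The partial factorial design makes 276 an upper figure.

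**6. Chance imbalance.** On a margin, the SE of a baseline difference is √(2/552.5) = 0.060 SD, so 95% of chance differences lie within 0.118 SD. A difference at that limit would move an unadjusted 18-month comparison by ρ × 0.118: 0.035 SD at a correlation of 0.3 and 0.083 SD at 0.7. The covariates already in the model absorb part of this.

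**The case against.** **It belongs in the SAP.** Outcome-specific covariates for secondary endpoints are often settled there, and 9.2 promises one. The clause on additional adjustments gives examples, not a closed list, so a baseline EQ-5D term would fit within it. This stands in part: the adjustment is unnamed, not ruled out. But 9.2 does commit to a named set, and a clause that applies where relevant and feasible commits to nothing. LACI-2, as described in section 1.1, added an outcome baseline only for cognition, so precedent does not settle the matter for quality of life.

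**The size rests on chosen inputs.** This stands. SD, difference and correlation are all assumed, and at ρ = 0.3 the gain is only 4 points. The correlation must be partial, after mRS, NIHSS, MoCA and age. Section 9.2 also gives deaths a score below any living score where a scale has no death category; that adds variance which baseline quality of life predicts poorly. Against this, section 4.3 excludes mRS above 2, so baseline mRS takes only the values 0 to 2 and is a coarse substitute for baseline utility.

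**Stronger readings that the documents do not support.**
- A reader might infer that the quality-of-life result would be biased by baseline imbalance. Under randomisation any imbalance is chance, it is small at this size, and the confidence interval already allows for it.
- A reader might infer that the plan gives up a known amount of power. No correlation is given, so no such amount can be stated.
- A reader might fault the concentration model for its covariates. Section 9.2 names no such model, and MoCA already adjusts for baseline cognition. What can be said is that a model should be named.
- A reader might extend the point to falls, which is on the baseline eCRF. Falls is listed as a symptom, and symptoms are analysed by binary logistic regression. The precision argument for linear models does not carry over.

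**Conclusion.** The point holds as a worthwhile improvement to a stated method, limited to secondary endpoints. Followed as written, 9.2 would probably give less precise estimates for EQ-5D-5L utility and EQ-VAS than the collected data allow. The estimates would still be valid.

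A plausible gain is from about 76% to between 80% and 87% power for partial correlations of 0.3 to 0.5, under the assumed SD of 0.25 and difference of 0.04 with 552 per group. It would be smaller if worst scores for deaths weaken the correlation, and negligible for an effect near 0.10. The primary outcome and the sample size are unaffected.

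**What to change.** In section 9.2, after the sentence on additional adjustments, state that the linear models for EQ-5D-5L utility and EQ-VAS also include the participant's baseline value of that measure, besides the stratification and minimisation variables. Then name a model for MMSE concentration and include its baseline value.

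The change need not extend to TICS, Zung or the Stroke Impact Scale, which are not among the baseline measures in 6.9 and 7.2, nor to falls.

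The cost is one or two sentences. The data are already on the baseline eCRF, participants have no added burden, and each model spends one more degree of freedom. Fixing the covariates now also limits later discretion in an open-label trial.
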